#### **Study Procedures**

Before the start of the study, participants underwent a screening measure where they

performed the ADAS-Cog-a neuropsychological test designed to assess the severity of cognitive impairment-to assess for cognitive impairment (Schafer et al., 2013). Another occupational therapy student researcher from the NKU Occupational Therapy program demonstrated competency in administering the ADAS-Cog under the supervision of a licensed occupational therapist prior to conducting the screenings. Participants who scored within the mild-to-moderate range (18–55) on the screening were eligible for admission into the study and proceeded to pretesting. Pre-testing and post-testing were conducted by a different NKU occupational therapy doctoral student, also supervised by a licensed occupational therapist, who had demonstrated competency in administering the Montreal Cognitive Assessment (MoCA) and The Observational Measurement of Engagement-Modified (OME-Modified) to minimize bias. The MoCA and OME-Modified were administered to participants as primary outcome measures to evaluate levels of cognitive impairment and engagement. The MoCA is a standardized tool that assesses cognitive domains: attention, executive functions, short-term and working memory, language, visuospatial, and orientation (Nasreddine, 2017). Scores range from 0 to 30, with scores of 18 to 25 indicating mild impairment, 10 to 17 indicating moderate, and 0 to 9 indicating severe (Nasreddine, 2017). The MoCA was selected due to its sensitivity to changes in cognition (Julayanont et al., 2013).

The OME-Modified assessed engagement through the assessment of a participant's response to a stimulus during an activity, taking note of their attention and attitude using standardized rating scales. The OME-Modified was selected due to its focus on the core outcomes, ease of use in an applied setting, high intra-class correlation value (.78), and high inter-rater reliability (0.84 - 0.92) (Cohen-Mansfield et al., 2010). Participants performed each assessment on alternate days to limit cognitive fatigue.

After screening and pre-testing were completed, the participants received CST in a group setting twice weekly, on Monday and Wednesday mornings, for 45 to 60 minutes each for 7 weeks. Sessions were co-facilitated by two doctoral occupational therapy students under the supervision of a licensed occupational therapist in the state of Indiana to ensure proper implementation of the intervention and adherence to professional and ethical standards.

Additionally, the co-facilitators were trained in CST by the North American CST Training Institute through the Saint Louis University School of Medicine prior to the start of the intervention. The general structure of each session followed the *Making a Difference 1* CST manual for consistency and accurate delivery of the intervention. Each session was based on a theme and included an introduction, theme song, current affairs activity, the main activity, and closure.

Based on previous research involving CST, there is no documentation of any harmful side effects following participation. Therefore, this indicates minimal risk of harm for participants who receive CST. However, there are potential risks of psychological and emotional effects during group participation, which could lead to feelings of anxiety, stress, and altered behavior. However, previous research has indicated that CST can improve psychological well-being in this population instead of causing harm/distress. There is also a risk that participants' identifiable information could be accidentally disclosed in a group setting.

Monitoring and Participation Forms from the *CST Making a Difference 1* manual were used to document attendance and session-level ratings of participant enjoyment, mood, interest, and communication (Spector et al., 2021). The forms were completed after each session by two occupational therapy doctoral students who co-facilitated the sessions. Participant ratings for enjoyment, communication, and interest were recorded on a 4-point scale of 1 (none) to 4 (lots)

(Spector et al., 2021). Mood was rated using a separate 4-point scale: 1 (anxious/depressed) to 4 (happy/relaxed) (Spector et al., 2021). The forms were not distributed to participants but were discussed at the end of each session. The feedback surveys involved participants raising their hands to indicate if they liked the session "a lot," "a little," or "not at all," followed by two open-ended questions: what they enjoyed and what could be improved (Spector et al., 2021). The CST Monitoring Forms data will be explored in a future retrospective study.

At the end of the 7-week period, participants performed the OME-Modified and MoCA for the posttest outcome measures again. During post-test administration of the OME-Modified, participants who demonstrated limited interest in the initial stimulus were retested using an alternative stimulus. This adjustment was made because the high stimulation of CST sessions may have reduced the appeal of the pre-test stimulus, potentially affecting the accuracy of results.

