#### **Participants**

Recruitment, data collection, consenting, and CST-related activities took place at Ridgewood Health Campus, including–Legacy Lane (memory care), the assisted living facility, and the health campus building, all located on the same site in Lawrenceburg, Indiana– using a convenience sampling approach. This is a facility owned and operated by Trilogy Health Services, LLC in Lawrenceburg, Indiana. Ridgewood Health Campus has facilities dedicated to memory care, skilled nursing, and assisted living. All facilities provide residents with apartments, 24/7 on-site healthcare staff, dining halls, transportation services, salons, indoor and outdoor common areas, and community gardens. Cognitive stimulation activities were held in the

memory care building (Legacy Lane) on the Ridgewood Health Campus. The memory care building includes open and accessible common areas that provide adequate space for conducting CST sessions without interfering with other facility operations. On-site nursing and medical staff were available as needed to support participant care. Researchers collaborated closely with facility staff to address any concerns related to the intervention, environment, or individual participants, ensuring the safety and well-being of everyone involved. In the event of an adverse incident during the study or treatment, researchers planned to follow HIPAA regulations and the facility's established protocols. Incidents were planned to be promptly reported to the Principal Investigator (PI) and the facility staff.

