#### Statistical Analysis Plan

Data were analyzed using IBM SPSS Statistics (Version 29). Demographic characteristics were analyzed using descriptive statistics. Normality of the data was assessed using the Shapiro-Wilk test, which indicated that the majority violated assumptions of parametric testing (Gil et al., 2022). A one-tailed Wilcoxon signed-rank test was conducted to assess pre- and post-intervention outcomes (Gil et al., 2022; Lok et al., 2020). To reduce a Type I error from multiple comparisons, a Bonferroni correction was applied to adjust the significance level to  $p \le .0045$  for the OME-Modified and  $p \le .05$  for the MoCA. Effect sizes (r) were calculated using  $Z/\sqrt{N}$  (0.1 = small effect, 0.3 = medium, 0.5 = large). Confidence intervals for r could not be computed due to sample size and software limitations. Due to the statistical probability of change in subtests, descriptive statistics were used to determine whether the performance in MoCA and OME-Modified subtests increased, decreased, or maintained.

Data inclusion was predetermined at 50% attendance, equivalent to attending at least two-thirds of each session and 7/14 sessions. Participants outside this criterion were classified as dropouts and excluded, with their data removed. This approach ensured that the analysis reflected outcomes from participants who meaningfully engaged in the intervention.

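### Low mood, incidents and stopping are left out of the planned analysis, and the 50% attendance exclusion could tilt the feasibility and tolerability picture towards no problem

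*Combined protocol and SAP*

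**What the plan says.** **The risk.** Study Procedures describes possible emotional effects of taking part in the group, "which could lead to feelings of anxiety, stress, and altered behavior". It judges the overall risk low from earlier research: "Therefore, this indicates minimal risk of harm for participants who receive CST".

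**The measurement.** The same section describes monitoring forms that record attendance and rate enjoyment, mood, interest and communication. "The forms were completed after each session by two occupational therapy doctoral students who co-facilitated the sessions". The lowest of the four mood scores stands for anxious or depressed.

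**The deferral.** Study Procedures then states: "The CST Monitoring Forms data will be explored in a future retrospective study".

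**The exclusion.** The Statistical Analysis Plan sets the threshold: "Data inclusion was predetermined at 50% attendance, equivalent to attending at least two-thirds of each session and 7/14 sessions". Anyone outside it is "classified as dropouts and excluded, with their data removed".

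**The analysis.** The Statistical Analysis Plan covers demographics, the MoCA and the OME-Modified. It plans no summary of mood, incidents, or numbers and reasons for stopping.

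**The incident route.** The Participants section adds: "Incidents were planned to be promptly reported to the Principal Investigator (PI) and the facility staff".

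**The concern.** Study Summary and Objectives makes feasibility the second aim. Who stops, and why, is core evidence for that aim, and so is how participants tolerated the sessions. The study collects a session-by-session rating close to the risk it names, but its own analysis does not use it.

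The exclusion makes the gap worse, because it can depend on the thing of interest. Ethical Considerations lets participants refuse any session or withdraw at any time. The threshold also asks for at least two-thirds of a session, so someone who leaves early because of anxiety may not be credited with that session. A distressed participant is therefore plausibly more likely than others to fall below 7 sessions. A feasibility or tolerability statement would then describe only the people who kept coming.

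**Working it through.** **1. The plan's own figure.** Study Procedures gives 2 sessions a week for 7 weeks: 2 × 7 = 14 sessions. The threshold is 7/14 = 50%, so the stated figure reproduces.

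**2. How much mood data is deferred.** The Participants section sets N = 10 and aims for 5 to 8 people per session. Full attendance would give 10 × 14 = 140 ratings. At the intended group size the range is 5 × 14 = 70 to 8 × 14 = 112. None enters this study's analysis.

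**3. What selective exclusion could do.** The documents give no distress rate and no dropout rate, so both are assumed here and shown as a range. Let p be the true proportion distressed and q the share of the distressed who fall below the threshold. The chance that at least one distressed participant of 10 remains in the data is 1 − (1 − p(1 − q))^10.

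| p (assumed) | q = 0 | q = 0.5 | q = 0.8 | q = 1 |
|---|---|---|---|---|
| 0.05 | 40% | 22% | 10% | 0% |
| 0.10 | 65% | 40% | 18% | 0% |
| 0.20 | 89% | 65% | 34% | 0% |
| 0.30 | 97% | 80% | 46% | 0% |

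Example: p = 0.20 and q = 0.5 give 1 − 0.90^10 = 0.651.

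**4. What the retained participants would show.** Assume also that 10% of non-distressed participants are excluded. The expected distress proportion among those retained is about p(1 − q) / [p(1 − q) + 0.9(1 − p)]. At p = 0.20:

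- q = 0.1 (same dropout in both groups): 0.18 / (0.18 + 0.72) = 20%, no bias
- q = 0.5: 0.10 / (0.10 + 0.72) = 12%
- q = 0.8: 0.04 / (0.04 + 0.72) = 5%
- q = 1: 0%

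The bias comes entirely from the distressed being excluded more often than the others.

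**5. What full reporting could show.** With no events in n participants, the one-sided 95% upper limit is 1 − 0.05^(1/n). It is 25.9% for n = 10, 31.2% for n = 8, 34.8% for n = 7 and 45.1% for n = 5. Including everyone helps, but 10 participants still cannot rule out a risk of about one in four.

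**The case against.** A reader might infer that the study cannot show harm even if it occurs, that dropouts' data are deleted, and that a distressed participant disappears from every result. The documents do not support this:

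- Incidents have a separate reporting route to the Principal Investigator and facility staff, and nothing in the Statistical Analysis Plan removes those reports.
- The mood ratings are put off to a later study, not discarded, and Data Collection and Management keeps data for six years.
- The removal rule stands in a section on the MoCA and OME-Modified analysis and can be read as exclusion from that analysis set. It does not mention destroying forms or incident reports.
- A participant with low mood who meets the attendance rule stays in.

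There are also substantive objections. The plan has no safety objective, and its statement of minimal risk rests on earlier research. One mood item covers the named risks only in part. No mood rating before the intervention is described, there is no control group, and the raters are unblinded facilitators, so a low score cannot be attributed to CST. The form also cannot follow someone who has stopped attending.

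All of this stands, and it limits what the ratings can prove. It does not remove the gap. Incident reporting is a notification route: the documents neither define an adverse incident nor plan a count, and a low mood rating need not qualify as one. Planned reporting of subtests that decrease concerns cognition and engagement, not mood. If the removal rule does reach the forms, the later study inherits the same selection. Because the forms cannot follow people who stop, the number and reasons for stopping need reporting beside the ratings.

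**Conclusion.** The concern holds in limited form. The planned analysis has no summary of low mood, incidents or stopping, although a risk is named, a related rating is collected at each session and feasibility is an aim. The attendance exclusion would bias the feasibility and tolerability picture towards no problem if distress drives people below the threshold. If it does not, that bias does not arise, but the reporting gap remains.

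The size of the bias is unknown. The tables above rest on assumed rates and illustrate the mechanism; they do not estimate it. The scope of the removal rule is unstated, which is itself a reason to clarify it. The documents do not support the reading that harm is undetectable or that evidence is destroyed. The change should be made, because the stated rules, and not only missing detail, produce the gap, and closing it costs little.

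**What to change.** 1. State in the Statistical Analysis Plan that the 50% attendance exclusion applies only to the MoCA and OME-Modified tests.
2. Add one descriptive table for everyone who began CST, including those under 50% attendance. It should give:
   - participants and sessions with a mood rating of 1, out of sessions attended;
   - incidents reported to the Principal Investigator;
   - the number who stopped or fell below 50% attendance, with reasons where recorded and a note where they were not.
3. Label the mood ratings as made by unblinded facilitators, uncontrolled, and not attributable to CST. Say that the table is descriptive only.

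The other form ratings can wait for the later study. The cost is a little analyst time and some overlap with that study. The mood and attendance records come from forms already completed; if the attendance rule is applied from those forms, they are already being opened for this analysis.

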#### **Study Summary and Objectives**

This research examined the effectiveness of CST while aiming to support and validate the role of occupational therapy and promote its integration into long-term care settings across the United States. Currently, there is limited research on occupational therapists implementing CST with older adults living with dementia in long-term care facilities. The purpose and aims of this research study were to: 1) investigate the preliminary effect of CST on cognition and engagement in individuals with mild-to-moderate dementia, and 2) assess the feasibility of implementing CST in LTC facilities in the Cincinnati metropolitan area. The objective of this research was to answer the following question: Does CST improve cognitive functioning and increase engagement levels in individuals with mild-to-moderate dementia residing in long-term care facilities? We hypothesized that individuals with mild-to-moderate dementia who participated in a 7-week CST program in a long-term care facility would exhibit significantly higher levels of engagement and cognitive functioning compared to baseline.

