#### Methods

A quasi-experimental, single-group pretest-posttest design was used to evaluate the effects of engagement and cognitive functioning in a group CST program. The study was

conducted as a student-led research project by occupational therapy doctoral students from Northern Kentucky University (NKU) who had completed their didactic coursework, including a group intervention course, and their first Level II fieldwork prior to engaging in on-site activities.

Although a randomized controlled trial (RCT) was initially planned, recruitment challenges, time constraints, and logistical limitations led to a modification of the study design. The modification addressed an ethical concern regarding the control group not receiving the intervention, as a delayed intervention was not logistically feasible for the researchers. Due to the nature of the study design, no blinding of participants or researchers occurred. The study was approved by NKU's Institutional Review Board for human subjects research (IRB # 2562) and revisions to the study protocol were approved prior to the start of the intervention. The study was registered at ClinicalTrials.gov (NCT06978972) and made public in June 2025. The study was conducted from May to August 2025 at a long-term care facility in southeast Indiana that provides memory care, assisted living (ALF), and skilled nursing (SNF) care. Data was collected between June and August 2025.

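### The OME-Modified, a primary outcome, was selectively repeated with a different stimulus at post-test only, and the analysis plan does not say which score is analysed

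*Combined protocol and SAP*

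**What the plan says.** Study Procedures gives the outcome its status: "The MoCA and OME-Modified were administered to participants as primary outcome measures". The same section describes the OME-Modified as rating attention and attitude in response to a stimulus, so the score depends on the stimulus used.

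On post-test administration the section says that "participants who demonstrated limited interest in the initial stimulus were retested using an alternative stimulus". It calls this step an adjustment and gives as the reason that the stimulating nature of the programme, in its words, "may have reduced the appeal of the pre-test stimulus, potentially affecting the accuracy of results".

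On who assessed, it says "Pre-testing and post-testing were conducted by a different NKU occupational therapy doctoral student", meaning someone other than the student who did the screening. Methods states that "no blinding of participants or researchers occurred".

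The Statistical Analysis Plan names a one-tailed Wilcoxon signed-rank test, a threshold of .0045 for the OME-Modified, the effect size r, and descriptive counts of subtests that rose, fell or stayed the same. It also sets an attendance rule for inclusion. It does not mention the retest.

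**The concern.** Engagement is half of the study's effect aim, which is to "investigate the preliminary effect of CST on cognition and engagement". With one group and no control, the inference rests on measuring pre-test and post-test in the same way. Here the trigger for a second measurement is a low value of the construct being measured. An unblinded assessor judged it without a written criterion, and it is described at only one of the two time points.

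A retested participant may have two post-test values, and the plan has no rule for choosing between them. Two analysts could therefore report different OME-Modified results from the same records. The choice feeds the one-tailed test, r and the descriptive summaries. The last two have no significance threshold to limit the effect of the choice.

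**Working it through.** **The plan's own figure.** The only stated design figure bearing on this outcome is the .0045 threshold. It matches .05/11 = .004545, although the plan does not state 11 comparisons. No figure is given for the retest: no trigger value, number retested, score SD or relative appeal of the stimuli.

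**What each scoring rule implies.** The plan names none of these.
- First score analysed: the retest has no effect.
- Better of the two kept: the value for a retested participant can rise or stay, never fall.
- Retest replaces the first score, or the two are averaged: low first scores are partly low by chance, so a second reading tends to be higher. The alternative's appeal adds to or subtracts from this.

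**Illustration of size. All inputs beyond the plan's are assumptions.**
- No true change, and one continuous normal score with SD 1.
- N = 10, the planned sample size.
- Pre/post correlation .78. This is the intra-class correlation cited in Study Procedures, which is not stated to be test-retest. Error variance is 1 − .78 = .22.
- The lowest share q of post-test scores is retested, with q from 10% to 50%. The documents give no count.
- The two stimuli are equally engaging.
- The correlation ρ between first score and retest is .78 if their errors are independent. If half the error variance is shared, for example because mood or alertness is the same, ρ = .78 + .11 = .89.

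With c the q-quantile of the standard normal and φ, Φ its density and distribution function:
- Replace: mean shift = (1 − ρ) × φ(c). Averaging gives half of this.
- Better kept: mean shift = the integral from −∞ to c of [mΦ(m/s) + sφ(m/s)]φ(x) dx, with m = −(1 − ρ)x and s = √(1 − ρ²).

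For q = 10%, φ(c) = .1755. For q = 50%, φ(c) = .3989.

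| Rule | ρ | 10% retested | 50% retested |
|---|---|---|---|
| First score | any | 0 | 0 |
| Replace | .78 | .22 × .1755 = +0.04 SD | .22 × .3989 = +0.09 SD |
| Replace | .89 | .11 × .1755 = +0.02 SD | .11 × .3989 = +0.04 SD |
| Better kept | .78 | +0.05 SD | +0.18 SD |
| Better kept | .89 | +0.03 SD | +0.12 SD |

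**When the direction reverses.** If the alternative differs in appeal by δ SD, the shift under replacement is qδ + (1 − ρ)φ(c). It is zero at δ = −(1 − ρ)φ(c)/q:
- Independent errors: −.22 × .1755/.10 = −0.39 SD at 10% retested and −.22 × .3989/.50 = −0.18 SD at 50%.
- Half the error shared: about −0.19 and −0.09 SD.

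The break-even is therefore not a fixed property of the design. It halves under an equally plausible error structure.

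**Effect on the test.** For N = 10 without ties, the exact signed-rank test at .0045 rejects when the negative rank sum is 2 or less. Its actual level is 3/1024 = .0029, about 0.3%. In simulation with independent errors and equal appeal, this rises to at most about 0.8% under replacement and about 2% when the better score is kept. The latter is more than four times the nominal .0045 (.02/.0045 = 4.4).

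**The case against.** The strongest reply is that the retest corrects a bias. If seven weeks of stimulating sessions made the old stimulus dull, the first post-test score understates engagement. The authors disclosed the step and their reason, the study is preliminary with ten participants, and nothing shows that the result was distorted. Much of this stands. Loss of appeal is a plausible bias in the opposite direction, and the documents do not size it either. But the text says only that appeal may have fallen, and re-measuring just the low responders at one time point does not apply the correction evenly. Disclosing the step also does not say which score was analysed.

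A fair criticism of the illustration is that independent errors overstate the shift when both readings share the day's mood or alertness. That is why both cases are shown. The retested share and the single continuous score are assumptions too. The OME-Modified uses rating scales, and the threshold suggests several comparisons, which the retest need not affect equally.

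A reader might infer that the retest score was used and that the engagement result is therefore inflated. Calling the step an adjustment points that way, but the documents do not say it. If the first score was analysed, there is no inflation from this source.

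**Conclusion.** The concern holds as a defect in how a primary outcome is defined. An outcome-triggered, post-test-only change of stimulus, made without blinding and without a scoring rule, leaves the OME-Modified post-test value not uniquely determined.

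The effect may be nil, upward or downward, and its net size cannot be derived from the documents. The directions are not equally likely: keeping the better score cannot lower the value, and replacing or averaging raises it unless the alternative is less engaging by more than the break-even amount. Under the assumptions listed, with equal appeal, the mean shift is between +0.02 and +0.18 SD across the replace and better-kept rules. The one-tailed error at .0045 stays at or below about 0.8% with replacement but can reach about 2% if the better score is kept. A stronger statement, that engagement gains were produced by the retest, is not supported.

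**What to change.** Make the first post-test administration, with the stimulus used at pre-test, the primary OME-Modified post-test value for every participant. Report the alternative-stimulus result as a labelled sensitivity analysis, with the number retested, how limited interest was judged, and both scores for each retested participant. State whether any retest took place at pre-test. List possible loss of appeal of the repeated stimulus as a limitation.

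If first-stimulus scores were not recorded for some retested participants, disclose this and base no OME-Modified efficacy statement on their retest values.

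If the first scores exist, the cost is a short addition to the Statistical Analysis Plan and a re-run of the OME-Modified comparison. If they do not, the cost is a disclosure and a narrower claim, because data collection is over. The downside is that the OME-Modified result may be less favourable and will keep any repeated-stimulus effect.
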